1. SUMMARY

The overarching aim of the programme 'Stimulating evidence based, personalized and tailored information provision to improve decision making after oesophagogastric cancer diagnosis' (SOURCE) is to provide oesophagogastric cancer patients at all disease stages with evidence based and personalized information about survival, treatment-related side-effects and/or complications and health related quality of life, tailored to patients' specific information needs, to facilitate informed decision making about treatment and thereby optimize personal care and outcomes. For this purpose the Source tool and training were designed. The Source tool is a prediction model based website to be used by care givers for informing patients about the outcomes of treatment. The Source training for care givers is designed to learn care givers how to inform patients effectively, especially about the outcomes of treatment.

The primary aim of the SOURCE trial is to investigate the effect of the tool and training on the (numerical) precision of information about outcomes of treatment in the treatment information consultation. Secondary outcomes include: patients' satisfaction, evaluation and knowledge of the information provided by the health care provider, evaluation of the decision made and health related quality of life.

A pragmatic stepped wedge design will be used to test the effect of intervention. 21 health care providers will include 3 patients as control measurements (before intervention) and 3 patients as intervention measurements (after intervention). Participating centers will be divided into geographical subgroups, in which the transition period (in which the intervention will take place) will be spread across time.

All oesophageal and gastric cancer patients scheduled for a treatment information consultation with a participating health care provider are suitable for inclusion and will be approached for participation in the SOURCE study. Measurements include audio recordings of the treatment information consultation and questionnaires filled in by patients and health care providers at different moments in time. Audio recordings will be scored and analyzed based on a study specific coding scheme. We estimate the physical burden/risk of this study to be negligible.

2. INTRODUCTION AND RATIONALE

Oesophagogastric cancer is a deadly disease with an increasing incidence (www.cijfersoverkanker.nl). Despite some improvement in survival, curative surgery results in a long-lasting deterioration in health related quality of life (HRQL).¹ In the palliative setting, half of the patients experience a loss in HRQL in the first 6 months after the start of chemotherapy.² Hence, improved survival may come with deterioration of HRQL. In the curative setting, patients consider quality of life of primary importance and they report it may outweigh survival when deciding about treatment options.³ Likewise, one in four patients with advanced cancer indicates that sustained or improved HRQL is their main treatment goal.⁴ To make well-informed treatment choices that match with patients' preferences, information about treatment outcomes, in terms of survival, treatment-related morbidity and HRQL is required. Currently, however, we lack good quality outcome data on

oesophagogastric cancer that could be used to provide patients with personalized information, accommodating the specifics of their clinical and sociodemographic situation.⁵ Also, physician's skills in providing evidence based information tailored to the specific information needs of patients merit improvement.^{6,7} Thus, we are unable to effectively provide oesophagogastric cancer patients with personalized information on treatment outcomes to facilitate shared decision making.

The overarching aim of the programme 'Stimulating evidence based, personalized and tailored information provision to improve decision making after oesophagogastric cancer diagnosis' (SOURCE) is to provide oesophagogastric cancer patients at all disease stages with evidence based and personalized information about survival, treatment-related side-effects and/or complications and HRQL, tailored to patients' specific information needs, to facilitate informed decision making about treatment and thereby optimize personal care and outcomes.

For this purpose, we designed the Source tool and training. The Source tool is a website to be used by care givers for informing patients about the outcomes of treatment. Prediction models are developed and built in the website in order to generate a personalized prediction of the outcomes: survival, toxicity and/or complications and HRQL. These predictions are visualized in clear and comprehensible graphs with a broad variation of options available for tailoring of the visualizations.

In order for care givers to be able to use this tool effectively, we designed the Source training. This communication skills training is comprised of an e-learning, two face-to-face group sessions and an individual booster session. Aside from an instruction video on the navigation within the Source tool, the e-learning consists of theory and tips and tricks on how to inform patients and communicate risks. The face-to-face components of the training are focused on getting the skilled use of the source tool into practice, by receiving personal feedback on the performance. Amongst the tackled problems are: how to tailor information to patients' needs, how to understandably communicate risk while not taking away patients' hope and how to use information in the context of a shared decision.

3. OBJECTIVES

We aim to test the effectiveness of the tool ('Source') and the communication skills training for health care providers.

3.1. The primary research question is:

Does the combination of the tool and the training improve observed (numerical) precision of information about treatment outcomes in clinical consultations?

3.2. The secondary research questions are:

Does the combination of tool and training affect:

- Health care providers' personalization of treatment outcome information
- Health care providers' tailoring of treatment outcome information
- Health care providers' use of visualizations
- Health care providers' setting the agenda
- Health care providers' use of time frame, initiative, treatment outcome category (on an utterance level)

- Health care providers' observed (numerical) precision of information about treatment outcomes in simulated patient consultations (effect training only)
- Health care providers' intention to inform patients about treatment outcomes using numbers (effect training only)
- Patient and physician satisfaction with communication and decision making
- Patient-reported shared decision making
- Patients' evaluation of the decision made
- Patients' evaluation and knowledge of the information provided by the health care provider
- Patients' health related quality of life
- Patients' trust in the health care provider
- Patients' anxiety
- Patients' helplessness/hopelessness
- Consultation time
- The (provisional) treatment decision made

Additionally we will assess:

- Demographical and personal variables
- Health care providers' use of the Source tool
- Health care providers' evaluation of the Source tool
- Health care providers' evaluation of the Source training + e-learning

4. STUDY DESIGN

4.1. Design

A multi-center pragmatic cluster stepped wedge design will be adopted. All health care providers will receive the intervention, i.e. the training and tool but at different time slots. These time slots are dependent on the geographical region (see Figure 1). Before the intervention takes place, a period of four to six months (taking the holiday season into account) will be used to include patients in order to collect control measurements. The subsequent transition period, in which the intervention will take place, will take approximately three to four months. After the intervention has taken place, again a period of four to six months is scheduled in which participating health care providers will include patients for measurements. Each participating health care provider (cluster) will include approximately three patients before and three patients after the intervention has taken place. The number of three patients per care provider is used as a mean, the minimum will be set at two patients and the maximum at six. The consultation with these patients will be audio recorded and providers and patients are asked to fill in short questionnaires before and after the consultation (see paragraph 7.2). In addition, each health care provider will do one simulated patient consultation before and one after training, which will also be recorded on audio.

4.2. Duration

Inclusion and data collection will take approximately 2 years. Figure 1 shows the planning of the study.

Region	oct-19	nov-19	dec-19	jan-20	feb-20	ma-20	apr-20	may-20	jun-20	jul-20	aug-20	sep-20
1			S	S			S	S	s			
2					S	S			S	S	S	
3										S	S	
4												
											Summer	
Region	oct-20	nov-20	dec-20	jan-21	feb-21	mrt-21	apr-21	may-21	jun-21	jul-21	aug-21	sep-21
1												
2												
3		S	S	S								
4		S	S			S	S					
											Summer	
Legend												
Control measurements												
Transition period												
Intervention measurements												
S = Simulated Patient Assessments												

S = Simulated Patient Assessments

Figure 1. A schematic representation of the study planning over time

4.3. Setting

The study will be conducted at the medical oncology, radiotherapy and surgical departments of both academic and peripheral hospitals in the Netherlands.

4.4. Design over time

Figure 2 shows the design of the study over time for health care providers.

Figure 2. A schematic representation of the study design over time for health care providers, SPA = Simulated Patient Assessment.

5. STUDY POPULATION

5.1. Population (base)

All patients in participating centers, who have been diagnosed with oesophageal or gastric cancer and are scheduled for a treatment information consultation, will be asked to participate. The treatment information consultation is defined as the consultation in which one of the health care providers' main goals is to inform the patient on the outcomes of treatment(s), for example when decisions about treatment have to be made. All oncologists, radiotherapists and surgeons (specialists and fellows), physician assistants and nurse practitioners conducting these consultations with oesophageal and gastric cancer patients, will be asked to participate.

5.2 Inclusion criteria

Health care providers:

- Specialist, physician assistant or nurse practitioner in the field of oncology, oncological radiotherapy or oncological surgery who are used to discussing treatment and treatment outcome with patients
- Informed consent for data collection
- Three audiorecorded treatment information consultations with oesophageal or gastric cancer patients before the scheduled transition period (control measurements)
- Three audiorecorded treatment information consultations with oesophageal or gastric cancer patients after the scheduled transition period (intervention measurements) and before the scheduled end date of the study

Patients:

- Age ≥ 18 years
- Histological or cytological proof of oesophageal or gastric cancer
- Informed consent for trial data collection

A treatment information consultation with a participating doctor to discuss either curative treatment, first line palliative treatment, and/or best supportive care.

5.3 Exclusion criteria

Health care providers:

- Less than two control and/or intervention measurements *Patients:*
- Cognitive impairment or insufficient understanding of the Dutch language
- GIST and smallcell tumors

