5.4 Sample size calculation

The intervention is considered successful if a significant difference is observed in the precision of information about treatment outcomes provided by the health care providers (primary outcome) before and after the intervention. Assuming a medium sized effect (0.5 SD), an intracluster correlation of 0 and a power of 80%, 21 health care provider , i.e. clusters, are needed with 6 patients per health care provider (3 control and 3 post intervention). Thus, in total 21 health care providers and 126 patients need to be included in the study. Based on a predicted response rate of 50 % 252 patients will be approached.

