7.4. Replacement of individual subjects after withdrawal

Participating patients will only be replaced after withdrawal if the minimum of 126 audio recoded consultations in total or the minimum of 2 control measurements and 2 interventions measurements per health care provider is not reached.

Participating health care providers that did not succeed in including 2 control measurements and 2 interventions measurements will only be replaced if the minimum of 21 in total is not reached. Health care providers who withdraw during the study will only be replaced if they drop out after informed consent, but before training.

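### A trained provider can be excluded on a recording count known only after training; separately, section 5.2 requires three recordings per phase where 4.1, 5.3 and 7.4 accept two

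*Protocol*

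**What the plan says.** Four sections of the protocol set a number of recordings per provider.

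- **5.2 Inclusion criteria** has two provider lines that each begin "Three audiorecorded treatment information consultations with oesophageal or gastric cancer patients". One covers the time before the transition period and the other the time after it, the latter ending "intervention measurements) and before the scheduled end date of the study". Neither line is softened by an average or an approximation.
- **4.1 Design** says that the figure of three "is used as a mean, the minimum will be set at two patients and the maximum at six".
- **5.3 Exclusion criteria** excludes a provider with "Less than two control and/or intervention measurements".
- **7.4 Replacement** uses a minimum of two per phase. It names the providers who "did not succeed in including 2 control measurements and 2 interventions measurements" as a group of their own, and its rule for this group is that they "will only be replaced if the minimum of 21 in total is not reached". Patients are replaced if "the minimum of 126 audio recoded consultations in total" or the per-provider minimum is not met. Providers who withdraw are replaced only if they leave before training.

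Section 4.1 places the intervention recordings after the transition period in which the training is given. Section 5.4 plans 21 providers with three patients in each phase, 126 in all, and adds: "Based on a predicted response rate of 50 % 252 patients will be approached". Section 9.1 compares the two phases in a within-subjects analysis.

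**The concern.** There are two points of unequal weight.

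**Wording.** A provider with two recordings in a phase fails 5.2 and satisfies 4.1, 5.3 and 7.4. Three sections give one working rule and 5.2 departs from it.

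**Eligibility after exposure (the main point).** The second recording line in 5.2 and the intervention half of 5.3 cannot be checked at enrolment or before training. A provider can be enrolled, supply control recordings, be trained, remain in the study, and then become ineligible because too few later consultations were recorded. Section 7.4 foresees this. It takes training as the cut-off for replacing providers who withdraw, but not for those who fall short. The floors of 126 recordings and 21 providers protect the numbers; they do not undo selection on what happened after training.

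At stake is the population to which the primary result applies. If falling short is related to how much a provider gained from the intervention, the effect in completers differs from the effect in all trained providers.

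**Working it through.** **1. The plan's own figure.** With a difference of 0.5 SD, ICC 0, 80% power and two-sided alpha 0.05 (5.4 states no alpha), n per phase = 2 × (1.960 + 0.842)² / 0.5² = 62.8, so 63. Then 2 × 63 = 126 = 21 × 6, which agrees. The sample size needs three per phase on average, as in 4.1, and not three from every provider, as in 5.2.

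**2. How often a trained provider would fall short.** From 5.4, 252 / (21 × 2) = 6 approached and 126 / 42 = 3 recorded per provider and phase. These are averages of trial totals; the protocol does not allot six approaches to each provider and phase. Assuming independent acceptances at 50%:

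| Approached per provider and phase | P(fewer than 2) | Of 21 |
|---|---|---|
| 6 | (1 + 6)/64 = 10.9% | 2.3 |
| 8 | (1 + 8)/256 = 3.5% | 0.7 |
| 10 | (1 + 10)/1024 = 1.1% | 0.2 |
| Poisson, mean 3 recorded | e⁻³(1 + 3) = 19.9% | 4.2 |

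Exactly one recording, which an analysis can still use, accounts for 6/7 = 86% of shortfalls in the first row and 75% in the last.

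**3. What exclusion could do to the estimate (illustration, either sign).** Let the effect in excluded providers differ from that in completers by d, with providers weighted equally. The shift is share excluded × d:

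- 10.9%: 0.109 × 0.25 = 0.027 SD and 0.109 × 0.5 = 0.055 SD
- 19.9%: 0.199 × 0.25 = 0.050 SD and 0.199 × 0.5 = 0.100 SD

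No value of d stands in the documents.

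**4. How much of this the fix recovers.** Take a random-intercept model without period effect, with nineteen 3+3 providers and two 3+1 providers.

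- At ICC 0 the two short providers supply 2 of 59 intervention recordings, a weight of 3.4%.
- At ICC near 1, provider information is proportional to ab/(a+b) for a control and b intervention recordings: 1.5 for 3+3 and 0.75 for 3+1. The weight is 1.5 / (28.5 + 1.5) = 5.0%.
- They are 2/21 = 9.5% of providers, so their weight is about 0.36 to 0.52 of their share.

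Change in the estimate = shift × proportion with exactly one recording × this ratio:

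- Lowest: 0.027 × 0.86 × 0.36 = 0.008 SD
- Highest: 0.100 × 0.75 × 0.52 = 0.039 SD

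That is roughly 0.01 to 0.04 SD, against a planned effect of 0.5 SD. Using the same ratio at the 19.9% rate is an approximation. At the 3.5% and 1.1% rates the change is smaller.

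**5. Precision.** Because 7.4 provides for replacement up to 21, the baseline is 21 complete providers, with two 3+1 providers added. At ICC 0, SE = √(1/63 + 1/63) = 0.178 becomes √(1/69 + 1/65) = 0.173, about 3.0% lower. At ICC 0.5 the same model gives 0.126 and 0.123, about 2.4% lower.

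**The case against.** **The count may be no more than a data-sufficiency rule.** A minimum of two per phase is a defensible choice for a within-provider contrast, and a provider with no later recording adds nothing to it. That stands for providers with none. It does not stand for those with one, who are most of the shortfalls under the assumptions above.

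**The analysis set belongs in the statistical analysis plan.** In general it does, and silence on it would be no finding. Here the protocol states a rule: a provider below the count meets an exclusion criterion. An analysis plan that kept such a provider would contradict 5.3 as written. It remains true that 5.3 does not say in terms what happens to the existing recordings; their loss follows only from a literal reading.

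**Shortfall may simply reflect caseload.** This carries weight. Section 5.1 has all scheduled patients asked, research staff make the telephone invitation (7.2.1, 10.1.3), and each consultation with a participating patient is recorded (7.2.2). Providers may identify patients, be asked to permit contact and operate the recorder (10.1.3), so their influence is real but limited.

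**Stronger readings.** A reader might infer that the before/after comparison is biased, or that the two phases contain different providers. The documents support neither. Both phases of an excluded provider are lost, so the phases stay matched, and nothing shows that shortfall is related to the effect. A reader might also take 10.9% as a protocol figure; it rests on an assumed cap of six approaches, and the rate falls quickly above that. Nor does the concern extend to the control count, which is known before training.

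**Conclusion.** Both points hold on the text. The conflict between 5.2 and the other three sections is a wording correction. The main point is that the intervention half of 5.2 and 5.3 makes eligibility depend on a post-training count, and so narrows the primary comparison to completing providers.

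The size is modest and uncertain. The expected number of trained providers affected runs from 0.2 to 4.2 of 21 across the assumptions shown, and more recruitment would lower it. The change in the estimate depends on an assumed difference in effect for which the documents give no evidence. The gain in precision is about 2.4% to 3.0%, under a random-intercept model and two 3+1 providers. Severity is minor to moderate: worth correcting because it removes a selection after exposure at the cost of wording, not because a material bias has been shown.

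**What to change.** - **5.2:** delete the two lines that require three recordings per phase.
- **4.1:** keep two to six per phase, mean three, as a recruitment target.
- **5.3:** remove the post-training count. If the control-phase minimum of two is kept, apply it before training, as a condition for entering it, so that 5.3 and 9.1 describe the same providers.
- **7.4:** allow an additional provider to be recruited when a trained one falls short, without dropping the trained one.
- **9.1:** base the primary analysis on all recordings from every provider who entered the training phase, in a multilevel model with a provider effect; analyse the 2+2 providers as a sensitivity analysis; report how many trained providers fell short.

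The cost is wording in five sections and no extra data. The downside is some unbalanced providers who add little information. A provider with no post-training recording still adds no within-provider effect, so the fix reduces the selection and does not remove it entirely.

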5.4 Sample size calculation

The intervention is considered successful if a significant difference is observed in the precision of information about treatment outcomes provided by the health care providers (primary outcome) before and after the intervention. Assuming a medium sized effect (0.5 SD), an intracluster correlation of 0 and a power of 80%, 21 health care provider , i.e. clusters, are needed with 6 patients per health care provider (3 control and 3 post intervention). Thus, in total 21 health care providers and 126 patients need to be included in the study. Based on a predicted response rate of 50 % 252 patients will be approached.

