9. STATISTICAL ANALYSIS

9.1. Primary study parameter

Audio tapes of consultations will be analyzed, using Noldus' The Observer XT software, on the primary outcome. Time-based analysis on all utterances of information on treatment outcomes is performed. Each utterance will receive a code based on the study specific coding scheme. Utterance scores will be summarized on the level of the consultation and compared between control and intervention measurements in a within-subjects analysis. Effects with one-sided p-values < .05 will be considered significant; 95Cl's as well as effect sizes will be provided. Baseline differences across the compared patient groups on socio-demographic (age, gender, educational level, etc.) and clinical characteristics (cancer phase at time of the consultation, time since diagnosis, etc.) as well as patients' baseline measures will be examined with the appropriate statistical tests (ANOVA, Chi-squared tests). All analyses of effectiveness will be controlled for specialization of the health care provider, profession of the health care provider (specialist, fellow, nurse specialist, physician assistant) and center specific characteristics (academical or peripheral hospital, starting time of intervention).

Reasons for missing data will be registered and recorded. Dependent on the type of missing data, the appropriate procedures will be used. If necessary, multiple imputation could be applied.

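### The 80% power in section 5.4 has no stated alpha, does not belong to the one-sided test in section 9.1, and makes no allowance for calendar time in the stepped wedge of section 4.1

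*Protocol*

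**What the plan says.** - **Sample size (5.4).** For an effect of 0.5 SD, with "an intracluster correlation of 0 and a power of 80" per cent, 21 providers (the clusters) are required, each with three control and three post-intervention patients, 126 in all. Success is framed as a significant before/after difference. The section gives no alpha, sidedness or formula, and does not mention steps, periods or time trend.
- **Significance rule (9.1).** "Effects with one-sided p-values < .05 will be considered significant". This is the only significance criterion in the protocol.
- **Primary contrast (9.1).** Consultation scores are "compared between control and intervention measurements in a within-subjects analysis". The adjustment list includes centre characteristics: "academical or peripheral hospital, starting time of intervention". No calendar-time or period term is listed.
- **Design (4.1, 4.2, Summary).** "A multi-center pragmatic cluster stepped wedge design will be adopted". Time slots depend on region, and "the transition period (in which the intervention will take place) will be spread across time". Control and intervention windows last four to six months each, with a transition of about three to four months between them. Figure 1 lists four regions, and "Inclusion and data collection will take approximately 2 years".

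**The concern.** A power figure has meaning only for a stated test under a stated model. Section 5.4 leaves the test unstated, and its number does not follow from the rule in section 9.1.

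A stepped wedge is staggered so that the intervention effect can be separated from change over time. Within each provider, every control consultation precedes every intervention consultation. Any secular change in how outcomes are discussed therefore enters a within-provider contrast in full. The start time of the intervention is one value per centre. It can absorb differences between centres, but it cannot remove a trend within a provider.

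Two things are at stake. One is whether a positive primary result can be told apart from drift. The other is whether the protocol's only power figure still applies once the analysis makes that distinction.

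**Working it through.** **Step 1: reproduce 126.** Inputs from 5.4: effect 0.5 SD, ICC 0, power 80%. The alpha is inferred. Per phase, n = 2(z_alpha + 0.8416)² / 0.5².

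- Two-sided 5% (z = 1.960): n = 62.8, so 63 v 63 = 126 = 21 × 6. This matches exactly.
- One-sided 5% (z = 1.645): n = 49.5, so 50 v 50 = 100. This does not match.

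One-sided 2.5% gives the same 126, so the inference concerns the critical value, not the wording. A plain two-group formula accounts for the whole number and leaves no allowance for steps or time.

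**Step 2: power under the rule in 9.1, no time term.** SE = √(2/63) = 0.178 SD.

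- Two-sided 5%: Φ(0.5/0.178 − 1.960) = 80.1%.
- One-sided 5%: Φ(0.5/0.178 − 1.645) = 87.7%.
- One-sided 5%, paired t test on 21 provider means: 85.6% at ICC 0, 88.7% at 0.1 and 91.7% at 0.2.

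For this contrast ICC 0 is conservative.

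**Step 3: add a linear calendar-time term at ICC 0.** The SE becomes 0.178/√(1 − R²), where R² is the squared correlation between intervention status and calendar time:

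R² = (g²/4) / (V + g²/4 + w²/12)

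Here w is the window length, g the gap between phase midpoints (window plus transition), and V the variance of region start dates. Section 4.1 gives g from 4 + 3 = 7 to 6 + 4 = 10 months. Assumptions: even accrual within windows, about 24 months in total, equal regions. With windows 4/3/4 the starts can span 24 − 11 = 13 months; with 6/4/6, 24 − 16 = 8 months. For four evenly spaced regions over span L, V = 5L²/36.

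One-sided 80% power needs SE ≤ 0.5/(1.645 + 0.8416) = 0.2011, so R² ≤ 0.215.

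| Windows (control/transition/intervention, months) and region starts | g | w | V | R² | SE | One-sided power |
|---|---|---|---|---|---|---|
| 5/3/5; starts 0, 3, 6, 9 | 8 | 5 | 11.25 | 0.545 | 0.264 | 60% |
| 4/3/4; starts 0, 2, 7, 11 (offsets of the first S marks in Figure 1) | 7 | 4 | 18.5 | 0.382 | 0.227 | 71% |
| 4/3/4; starts 0, 4, 8, 12 | 7 | 4 | 20.0 | 0.365 | 0.224 | 72% |
| 4/3/4; four even over 13 months | 7 | 4 | 23.47 | 0.331 | 0.218 | 74% |
| 6/4/6; four even over 8 months | 10 | 6 | 8.89 | 0.678 | 0.314 | 48% |
| 4/3/4; half the providers at each end of 13 months | 7 | 4 | 42.25 | 0.219 | 0.202 | 79.8% |

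Generalised least squares runs with a provider random intercept, several assumed layouts and a linear, quarterly or half-yearly time term gave about 60-73% at ICC 0.

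**Step 4: role of the ICC once time is in the model.** With a provider random effect and linear time, power falls as the ICC rises. From ICC 0 to 0.2 it goes from 74% to 69% (four even regions, 4/3/4) and from 71% to 64% (S-mark offsets, 4/3/4). ICC 0 is then the favourable end of the range.

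**Step 5: how far the layout matters.** Relaxing the assumptions of Step 3:

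- Half the providers at each end, 24.2 months in total: span 13.2, V = 6.6² = 43.56, power 80.0%. At 25 months: V = 7² = 49, power 80.8%.
- Consultations only in the two months on either side of a three-month transition (g = 5, w = 2): 80.3% for four even regions over 13 months, 83.5% with half the providers at each end.

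**Step 6: size of a possible bias.** The documents give no drift. For an assumed drift d in SD per year, bias = d × g/12 and one-sided error = Φ(bias/0.178 − 1.645). Over g = 7 to 10 months the error is 7-8% at d = 0.05, 9-12% at d = 0.1 and 16-24% at d = 0.2, against a nominal 5%.

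**The case against.** The strongest reply is that 5.4 contains no arithmetic error. Its number reproduces exactly, and 5.4 and 9.1 plan the same before/after contrast. For that contrast 80% is a safe figure and ICC 0 is conservative. The power loss arises only in a model that the protocol does not specify, and the detail of a model is commonly left to the SAP. This stands as far as it goes: the trial is not underpowered for the analysis written in 9.1. It does not answer the point that 9.1 itself fixes the contrast, the significance rule and the list of adjustments, and that these do not use the staggering for which the design in 4.1 is named.

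A reader might also infer from the 79.8% in Step 3 that 126 patients can never reach 80% once time is adjusted for. The documents do not support that. The two years and the transition length are both approximate, accrual within windows is not stated, 7.4 treats 126 as a minimum, and Step 5 shows layouts at or above 80%. The 48% is not a forecast either. It needs the longest windows with starts spanning only 8 months, whereas the first S marks lie 11 months apart.

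Finally, no particular inflation of the error rate can be claimed, because every drift value in Step 6 is assumed.

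**Conclusion.** The point holds in a limited form. Section 5.4 states a power without an alpha or sidedness. The number matches an inferred two-sided 5%, and under the one-sided .05 of 9.1 the same unadjusted contrast has about 86-88% power, a mismatch in the safe direction.

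The calculation makes no allowance for steps or calendar time, and the planned contrast is confounded with calendar time. With time in the model, one-sided power at ICC 0 would probably be below 80%: roughly 60-74% for plausible four-region layouts and lower with the longest windows. It comes near or above 80% only for extreme layouts or accrual bunched next to the transition. These figures rest on even accrual, about 24 months in total and assumed region starts, since the shading of Figure 1 cannot be read here. The direction is firmer than the size.

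**What to change.** Keep 21 providers and 126 patients, and make four changes.

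1. In 5.4, state the alpha and sidedness and make them agree with 9.1.
2. In 5.4, say that the 80% refers to a before/after contrast at ICC 0 without adjustment for time.
3. In 9.1, specify the primary analysis as a mixed model with a provider random effect and a calendar-time term.
4. In 5.4, restate the power or the detectable effect for that model over a range of ICCs, for example 0 to 0.2, using the real Figure 1 schedule and the significance level of 9.1.

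The work is one recalculation, one rewritten paragraph and one change to the model. The price is a wider confidence interval for the primary effect and probably a stated power below 80%. With the sample size held, that should be reported openly as the precision the design can give.
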